- [name], Chief Paediatric Radiologist

Central Hospital of Päijät-Häme, Department of Surgery

[name]

- [name], PhD, Orthopaedic Surgeon

Clinical Investigation Plan

Bioabsorbable Intramedullary Nail Fixation of Forearm Fractures in Children

Synopsis

Name of Sponsor: Bioretec Ltd.
Name of Medical Device: Bioabsorbable Intramedullary Nail
Title of Study: Bioabsorbable Intramedullary Nail Fixation of Forearm Fractures in Children
Investigators: 
○ [name], PhD, Associate Professor, Paediatric Surgeon○ [name], PhD, Orthopaedic Surgeon○ [name], Statistician○ [name], MB, PhD candidate○ [name], Paediatric Radiologist○ [name], Professor, MD, PhD, Paediatric Orthopedist and Surgeon○ [name], [name], PhD, Paediatric Orthopedist and Surgeon
Study Centres: 
- Oulu University Hospital, Department of Children and Adolescents- Central Hospital of Päijät-Häme, Department of Surgery, Unit of Paediatric Surgery
Studied Period (weeks): 52 (follow up 2 years) Date of First Enrolment: 2010 Date of Last Completed: 2018
Objectives: 
Primary objective: Clinical outcome of the fracture treatment is equal between patients treated by the new bioabsorbable medical device and by standard of care using a titanium alloy device. This will be assessed by functional and clinical outcome measuring range of motion of forearm, wrist and elbow and pain assessment at two-years' follow-up.
 
Secondary objective: The new medical device (bioabsorbable intramedullary nail) is at least as good as the routinely used device (elastic stable titanium alloy intramedullary nail) in forearm fracture treatment to achieve a level of reduction and stabilisation that is appropriate to the age of the child. This will be assessed by radiological outcome and determination of bony union formation and alignment in the healing forearm fracture using radiographic methods; further, soft-tissue and bone-tissue reactions are to be evaluated by MRI.

Methodology:

Clinical Investigation Plan

Bioabsorbable Intramedullary Nail Fixation of Forearm Fractures in Children

The fracture is fixed using the new medical device (bioabsorbable intramedullary nail) or the standard titanium intramedullary nail.

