Number of Patients: At most 2 pilot operations / study centre + Planned 13 operations required for analysis; Total 35 patients to be enrolled, appreciating the potential drop-outs.

Diagnosis and Main Criteria for Inclusion and Exclusion:

Diagnosis:

Children with an unstable midshaft (diaphyseal) forearm (radius and/or ulna) fracture.

Main inclusion and exclusion criteria: The subject and/or guardian has signed and dated the informed consent, the subject is 5 to 16 years of age, the subject has no previous fracture or infection of the study region, no metabolic bone disease, no systematic disease or medication affecting bone quality or resistance to infection.

Medical Test Device installation and identification:

The device is surgically implanted. The batch of device is identified by test device name, packaging date and clinical investigation number A2228-CIP-1.

Duration of Treatment:

The follow-up of the patients will be 104 weeks (2 years). The control device will be removed 6 months after operation. The bioabsorbable device is expected to retain its mechanical functionality for at least 8 weeks, while the complete bioabsorption of the device in human body is expected to take place within approx. 2 years.

Criteria for Evaluation:

Repeated examination of functional, clinical and radiographic outcome, and bone union formation by range of motion measurement, radiography (plain radiographs). Magnetic resonance imaging for a randomly selected subgroup of at least 10 patients treated by test device, general questionnaires.

Efficacy:

The success of fixation will be determined by radiographic measurements in comparison between the immediate postoperative state and 6, 12 and 26 weeks after surgery.

Safety:

Continuous evaluations of safety parameters and specific evaluations of adverse events and serious adverse events will take place at each postoperative study visit. The safety variables to be evaluated include adverse events, findings from physical and radiographic examinations, subjective reports of pain and functional outcome assessments.

Statistical Methods:

The primary variable will be analysed using an analysis of variance model for repeated measurements. Treatment differences with 95% confidence intervals will be calculated from the model.

Identification of the Investigational Device

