Investigational devices for intramedullary nail fixation are manufactured by Bioretec Ltd. Devices are intended for forearm fracture repair of radial and/or ulnar shaft. The main purpose of the device is to achieve a level of reduction and stabilisation of fracture that is appropriate to facilitate the uneventful bone healing, thus restoration of the pre-trauma anatomical structure, taking into account the age of the child. In addition, the need for the second operation to remove hardware will be obviated by the investigational devices.

Devices are made of bioabsorbable oriented high-strength poly(lactide-co-glycolide) (PLGA) 85:15. The diameter of the IM nails is 2.0 mm, 2.7 mm or 3.2 mm. The nails are 400 mm long and in the tips of the nails there are x-ray positive markers. The high strength of IM nails is result of special orientation techniques applied in the manufacturing of the products at Bioretec Ltd. The corresponding shorter product, ActivaPin™ is registered product, which has been on the EU and US markets already several years.

Prior training in the insertion techniques of bioabsorbable devices is recommended.

Identification of the Control Device

Commonly used titanium elastic nail (TEN) manufactured by SynthesDePue Inc. is used as a control device in this study. According to routine clinical practices, the control device LOT number is documented into CRF. The main purpose of the device is to achieve a level of reduction and stabilisation of fracture that is appropriate to facilitate the uneventful bone healing, thus restoration of the pre-trauma anatomical structure, taking into account the age of the child. Prior training in the insertion techniques of TEN nails is recommended.

Preliminary Investigations and Justification of the Study

The purpose of this prospective, randomized clinical trial is to assess the efficacy and safety of a bioabsorbable device in fixation of forearm fracture patients. As the primary endpoint, the bioabsorbable intramedullary nail is expected to act as efficiently as the routinely used TEN nails in stabilization of forearm fractures in pediatric patients with unstable radius and/or ulna fractures.

Literature Review

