The primary objective of the study is to evaluate the feasibility and efficacy of the new medical device in treatment of paediatric patients with forearm fractures. The key variables in this assessment are the evaluation of the functional and clinical outcome by measuring range of motion in forearm, wrist and elbow (e.g. measuring supination/pronation and flexion-extension movements), and subjective pain assessment during recovery. The primary objective will be met if these outcomes in the treatment group are at least comparable to those of the patients treated with standard of care (TEN nail), interpreted by using the Price's classification system (<15 degrees of change in motion range is excellent clinical outcomes), and Flynn's criteria for upper extremity assessment (<10 degrees of change in motion range justifies satisfactory outcomes). The potential difference less than 10 degrees are to be determined not clinically significant. The raw results of clinical measurements and statistical significance of each finding are to be reported.

Secondary Objectives

The secondary objectives of the study are to evaluate the radiographic outcome of the forearm fracture treatment in patients treated using the study device. The key variables in assessment of these objectives are:

- fracture reduction and angulation,
- formation of bridging callus and consolidation (union, delayed union, non-union and malunion)

The method in assessment of key variables is plain radiographic evaluation. The secondary objective will be met if these outcomes in the treatment group are at least comparable to those of the patients treated with standard of care (TEN nail). According to the previous literature, angular deformity of <10 degrees in radius and/or ulna is to be determined not clinically significant [27-29].

Soft-tissue reaction against the biodegradable implant are to be studied by Magnetic Resonance Imaging (MRI) for a randomly selected sub-group of at least 10 patients.

Design of the Clinical Investigation

Type and Design of The Study

This is a randomized parallel-group **two-centre** study on the use of bioabsorbable intramedullary nail device for fixation of the radial and ulnar shaft fractures in children. All patients will receive the standard of care for other injuries caused by the trauma.

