1.1.11 Primary Performance Variable

Evaluation of functional and clinical outcome consists of following determinations:

Clinical Investigation Plan

Bioabsorbable Intramedullary Nail Fixation of Forearm Fractures in Children

- Measurements of the range of motion (ROM) in the forearm, expressed as degrees \pm SD
 - Loss of supination and pronation of the forearm (graded according to the table below),
 - Loss of flexion and extension of elbow and
 - Loss of dorsiflexion and palmar flexion of the wrist, graded according to the Flynn's criteria (<10 degrees of change are excellent or good i.e. satisfactory; >10 degrees of change are fair or poor i.e. unsatisfactory); and Price's classification.
- General pain and pain at fracture site assessed by VAS, expressed as mm \pm SD
 - Duration of post-operative medication for pain

Table 1 Classification of outcome, graded using a system described by Price [25]

Outcome	Loss of Forearm Rotation and Symptoms
Excellent	$\leq 15^\circ$ loss of forearm rotation and no complaints with strenuous activity
Good	A loss of forearm rotation of 15° to 30° and only mild complaints with strenuous physical activity
Fair	A loss of forearm rotation of 30° to 90° and mild complaints during activities of daily living
Poor	All other outcomes

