1.1.14 Other Variables

Other variables documented in CRF are:

- Operation time
- Number of days lost from usual activities
 - Parents lost working days
- Length of hospitalization stay
- Complaints in daily living
- Esthetics

Statistics

Recommended statistical methods will be applied. All deviations made after approval of the CIP will be described and justified in the final study report.

Sample Size Considerations

Primary outcome variable in this study is loss of supination and pronation within 6, 12, 26, 52, and 104 weeks after surgery. The non-inferiority margin is set to be 80 % in the calculations (=Power).

It is previously known that the forearm pronation in this age group is 81.2 degrees (95% CI 79.6-82.28) and 79.6 degrees (95% CI 78.8-80.4) in girls and boys, respectively. The corresponding supination archs are 90.0 degrees (95% CI 88.0-92.0) and 87.8 degrees (95% CI 85.7-89.9). [26] The standard deviation (SD) is 6.1 degrees in pronation and 7.6 degrees in supination. We determined that the new method (ActivaNail –intramedullary fixation) should

Clinical Investigation Plan

Bioabsorbable Intramedullary Nail Fixation of Forearm Fractures in Children

result to the forearm rotational range of motion that is not more than 15 degrees lower, compared to the rotational range of motion in TEN group, according to the Price's classification (<15 degrees of decrease refers to excellent outcome).

Difference between means in the groups is set as 7.0 and the Alpha as 0.05. The sample size is estimated to be 13 experimental subjects and 13 controls according to an unpaired two sample Student t test. This study population will also be exclusively large enough to recognize decrease in the ROM that is clinically significant (>15 degrees of decrease in supination or pronation in ActivaNail compared to TEN group).

Statistical Hypothesis

The following hypothesis will be tested for the primary efficacy variable:

H₀: Investigational device is inferior to comparative devices

H₁: Investigational device is non-inferior to comparative devices

The non-inferiority limit is set to 80 %. Thus, non-inferiority is shown if the upper limit of the 95% confidence interval for the difference is less than or equal to 5 %.

Statistical Methods

All operated subjects who reach the 2-year follow-up will be included in the statistical analysis. Study data will be tabulated by treatment groups with descriptive summary statistics.

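### The protocol names conflicting primary outcomes and time points, so the same data can meet the sample-size section's definition and miss the success rule in Section 8.1

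*Protocol*

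**What the plan says.** The protocol describes the primary outcome in several places.

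- **Synopsis, primary objective:** "measuring range of motion of forearm, wrist and elbow and pain assessment at two-years' follow-up".
- **Section 8.1:** the key variables are "measuring range of motion in forearm, wrist and elbow (e.g. measuring supination/pronation and flexion-extension movements), and subjective pain assessment during recovery". The rule follows: "The primary objective will be met if these outcomes in the treatment group are at least comparable to those of the patients" on standard care. It is read through both the Price and the Flynn systems, with limits given only in degrees.
- **Section 1.1.11, Primary Performance Variable:** loss of supination, pronation, elbow flexion and extension, and wrist dorsiflexion and palmar flexion; then "General pain and pain at fracture site assessed by VAS"; then duration of pain medication. Table 2 adds subjective result under its primary heading.
- **Section 10.1:** "Primary outcome variable in this study is loss of supination and pronation within 6, 12, 26, 52, and 104 weeks after surgery".
- **Section 7:** "As the primary endpoint, the bioabsorbable intramedullary nail is expected to act as efficiently as the routinely used TEN nails in stabilization". The synopsis places stabilisation under the secondary objective, assessed radiologically.

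Sections 10.2 and 10.3 then test and analyse one primary variable, in the singular. Nothing states that Section 10.1 replaces the rule in Section 8.1.

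**The concern.** A non-inferiority claim needs one variable (or a stated combination), one time and one margin, fixed in advance. Here the section that says when the objective is met uses a wider set of outcomes than the section that sizes the trial. If the nails are comparable on rotation but the test device is worse on wrist motion or pain, Section 10.1 supports success and Section 8.1 does not. The trial is unblinded by design, so leaving the deciding outcome open until the data are seen is a particular weakness.

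**Working it through.** **1. The definitions side by side**

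| Place | Variable | Time |
|---|---|---|
| Synopsis, primary objective | Forearm, wrist and elbow motion; pain | Two years |
| 8.1 | Same family, with a success rule | Recovery period |
| 1.1.11 and Table 2 | Six movements, two VAS pain items, medication duration, subjective result | Table 2 visits |
| 10.1 | Supination and pronation | Weeks 6, 12, 26, 52, 104 |
| 7 | Stabilisation | None given |

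Table 2 schedules motion at weeks 4, 12, 26 and 104. It has no 6-week visit, and week 52 is a call without motion measurement. Two of the five times in Section 10.1 therefore have no planned motion data.

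Pain has no criterion. The limits in 8.1 are in degrees. The Price grades in 1.1.11 mention complaints with activity, but no limit is set for VAS pain or for a between-group difference in it.

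**2. The protocol's own sample size**

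Inputs from 10.1 and 10.3: difference 7.0, two-sided alpha 0.05, power 80%, unpaired t test, SD 6.1 (pronation) and 7.6 (supination).

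- SD 6.1: the t test gives 12.96, so 13 per arm; power at 13 is 80.1%. The stated 13 reproduces.
- SD 7.6: the t test gives 19.5, so 20 per arm; power at 13 is 61.5%.

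The stated number thus fits one movement of the narrowest definition. No SD is given for elbow, wrist or pain, so the wider definition cannot be sized from the document.

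**3. How often two definitions disagree**

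Assumptions: 13 per arm, no true difference, SD 7.6 for all six movements, pass if the upper 95% limit for the difference in loss is below the margin. For one movement:

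- SE = 7.6 × √(2/13) = 2.98
- Power = P(T > 2.064), T noncentral t with 24 df and noncentrality margin/SE
- Margin 10: 10/2.98 = 3.36, power 0.896
- Margin 15: 15/2.98 = 5.03, power 0.998

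With independent movements:

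- Margin 10: both rotations 0.896² = 0.80; all six 0.896⁶ = 0.52; passes the first and misses the second 0.80 − 0.52 = 0.28
- Margin 15: 0.998² = 0.996; 0.998⁶ = 0.988; difference 0.008

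Simulation with correlated movements:

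| Margin | Correlation | Both rotations pass | All six pass | Discordant |
|---|---|---|---|---|
| 10 | 0 | 0.801 | 0.519 | 0.282 |
| 10 | 0.3 | 0.814 | 0.600 | 0.213 |
| 10 | 0.5 | 0.827 | 0.667 | 0.160 |
| 10 | 0.8 | 0.850 | 0.761 | 0.089 |
| 15 | 0 to 0.8 | 0.996 to 0.997 | 0.987 to 0.992 | 0.009 to 0.005 |

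**4. A single data set**

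The 95% half-width is 2.064 × 2.98 = 6.2 degrees. Suppose the observed group difference is 0 for each rotation and 4 degrees for one wrist movement. The upper limits are 6.2 and 10.2. At 10 degrees the rotations pass and the wrist fails; at 15 degrees all pass.

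**The case against.** The strongest reply is that the statistics section does settle the tested domain. Section 10.1 names supination and pronation, Sections 10.2 and 10.3 speak of one primary variable, and the Price limit of 15 degrees concerns forearm rotation. The broad text would then be an objective, and Section 7 a loose phrase in the justification. Much of this stands: it would be wrong to say that no tested variable is named, and Section 7 gives no measurement or test. But Section 8.1 states when the objective is met, and no text withdraws it. A separate statistical analysis plan would not remove the contradiction from the protocol.

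Three stronger readings are tempting and are not supported.

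- A reader might count radiographic success as a further primary definition, because the synopsis says under Efficacy: "The success of fixation will be determined by radiographic measurements". It is never called primary there, and Section 8.2, Table 2 and Section 1.1.12 all treat radiographic outcomes as secondary.
- A reader might infer that any one comparable outcome suffices and that the false-claim rate is inflated. Section 8.1 asks for the outcomes in the plural, and nothing says that one is enough.
- A reader might multiply 80% power across all the outcomes and conclude that power collapses. That assumes independence and 80% for each. At 15 degrees the six movements jointly have about 99% power under the assumptions above; at 10 degrees it is about 52% if they are independent.

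**Conclusion.** The concern holds as a conflict between stated definitions of the primary outcome and its timing. Data can meet Section 10.1 and miss Section 8.1. For movements alone, the practical size is about 9% to 28% of trials at a 10-degree margin and under 1% at 15 degrees, assuming 13 per arm, no true difference and SD 7.6 throughout. Pain is left out of these figures and could add disagreement. The protocol does not settle which case applies: 8.1 treats differences below 10 degrees as not clinically significant, 10.1 uses 15 degrees, and 10.2 gives 80% and 5%. Stabilisation in Section 7 is a label to correct rather than a workable competing rule.

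**What to change.** - Make loss of forearm rotation, the variable Section 10.1 already names, the only primary variable. Assess it at 104 weeks, against one margin in degrees.
- State whether supination and pronation are summed or must each pass. Section 10.1 speaks both of rotational range and of a decrease in either movement.
- Align the synopsis, Section 8.1, Table 2, Section 1.1.11 and Section 10.1. Elbow, wrist, pain, medication duration and subjective result become secondary and do not decide the primary objective.
- Remove the primary-endpoint label from stabilisation in Section 7.
- Match the time points in Section 10.1 to the visits at which motion is measured.

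**Cost.** No new measurements are needed, but this is not wording alone, because power must be restated for the chosen variable and margin. With 13 per arm and no true difference:

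| Primary variable | Margin 15 | Margin 10 |
|---|---|---|
| Total rotation, SD √(6.1² + 7.6²) = 9.75 (uncorrelated) | 96% | 71% |
| Total rotation, SD 11.9 (correlation 0.5) | 87% | 54% |
| Both must pass, SD 6.1 and 7.6 (independent) | 1.000 × 0.998, over 99% | 0.980 × 0.896 = 88% |

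The correlations are assumptions; the protocol gives none. With total rotation and a 10-degree margin, the sample size would have to be revisited.

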The conventional level of 5% will be considered the level of statistical significance. All tests will be two-sided. Accordingly, 95% confidence intervals will be used.

Normality assumptions will be checked using normal probability plot for residuals. The use of transformation for a particular variable will be decided after examining the assumptions with the original scale of measurement. Analysis may be repeated without possible outliers.

The primary variable will be analyzed using an analysis of variance model for repeated measurements. Treatment differences with 95% confidence intervals will be calculated from the model. If the assumptions for the parametric models are not met suitable non-parametric models will be used.

Clinical Investigation Plan

Bioabsorbable Intramedullary Nail Fixation of Forearm Fractures in Children

Adverse Events

The safety variables to be evaluated include adverse events (AE), findings from physical and radiographic examinations, subjective reports of pain and functional outcome assessments. Further, all drop-outs will be reported. The adverse event data will include the following displays:

- AEs categorized by body system
- AEs categorized by severity grades 1-4 (mild, moderate, severe, life-threatening)
- AEs involving the region under study (RUS) specifically:
 - Fracture delayed union, nonunion and malunion
 - Hardware failure
 - Infection

All Serious Adverse Events (SAE) will be reported within 24 hours to the Sponsor. The SAEs include death, life-threatening event, medically important event, device malfunction, hospitalization, accidental exposure, persistent disability or incapacity, and cancer. In emergency SAE cases, the patients are requested to seek help in the Emergency room of the University Central Hospital. Any adverse events and their effects are reported using Case Report Form (CRF).

Quality Management

Monitoring Arrangements

The sponsor is responsible for the monitoring of this study. The principal investigator will provide sponsor with the data recorded during the study without personal identification data to allow the sponsor to check the compliance of the study with the CIP. The sponsor will appoint a monitor for assessing the investigator's compliance with the Clinical Investigation Plan and for performing source-data verification. A monitoring plan and report will be prepared.

Data Management

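### The secondary objective can be declared met on fracture union with no margin or confidence-limit rule, and 13 to 17 children per arm cannot support the claim

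*Protocol*

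**What the plan says.** Section 8.2 (Secondary Objectives) lists two groups of radiographic variables: reduction and angulation, and callus formation and consolidation, the latter classed as union, delayed union, non-union or malunion. It then gives a success rule: "The secondary objective will be met if these outcomes in the treatment group are at least comparable" to those of patients treated with the titanium elastic nail. The synopsis words the same objective as showing that the new device "is at least as good as the routinely used device".

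For angulation, section 8.2 adds a reading aid: "angular deformity of <10 degrees in radius and/or ulna is to be determined not clinically significant". Nothing similar is given for the union categories.

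Section 10.2 states a non-inferiority hypothesis, judged on a 95% confidence limit, and introduces it for the primary efficacy variable only. Section 10.3 applies the repeated-measures model, with treatment differences and 95% intervals, to the primary variable. The general rules in 10.3 are a 5% significance level, "All tests will be two-sided", and the use of 95% confidence intervals. No test is named for the secondary variables.

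**The concern.** The objective asserts that the new nail is no worse than the standard one, so it needs a stated largest acceptable excess and a confidence limit to compare with it. For union the protocol has neither. The decision tool it does state in general terms is a two-sided test of difference, which answers another question. In a small trial such a test usually fails to reject, and that is easily reported as comparability.

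This matters because section 5 gives stabilisation that allows uneventful bone healing as the device's main purpose, and section 8.2 is the objective that addresses it. The number of children was chosen for forearm rotation, not for union. Left as it stands, the rule invites a statement about union that the data could not bear out.

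**Working it through.** **1. What the sample size was built for.** Section 10.1 gives a difference of 7.0 degrees, alpha 0.05, 80% power, and a standard deviation of 6.1 degrees for pronation. For a two-sided unpaired t test at n = 13 per arm, the noncentrality is (7/6.1) × √(13/2) = 2.93 on 24 degrees of freedom, and power is 80.1%. Solving for 80% gives n = 12.96, so the plan's 13 per arm is reproduced. Union does not enter the calculation.

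**2. Inputs for union.** Per-arm sizes are 13 (the stated minimum) and 17 (35 enrolled, 35/2 = 17.5, rounded down, with no losses). The documents give no union-failure rates. I assume 5% in the control arm and 20%, 30% or 40% in the test arm.

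**3. How often a difference test would be non-significant.** The probability is the sum, over all counts t and c, of Bin(t; n, pT) × Bin(c; n, pC), taken where the result is not significant at two-sided 5%.

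| Assumed true rates | Fisher, n = 13 | Fisher, n = 17 | Newcombe interval includes 0, n = 13 | Same, n = 17 |
|---|---|---|---|---|
| 20% vs 5% | 94.6% | 88.4% | 85.9% | 77.0% |
| 30% vs 5% | 79.9% | 65.3% | 63.7% | 49.7% |
| 40% vs 5% | 57.6% | 39.3% | 39.6% | 26.0% |

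The uncorrected chi-square test gives the same figures as the Newcombe columns to the precision shown.

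**4. One data set, two answers.** Take 4 of 13 failures against 0 of 13.
- Fisher: p = 2 × C(13,4)/C(26,4) = 2 × 715/14,950 = 0.096.
- Uncorrected chi-square: 26 × (4 × 13 − 9 × 0)² / (13 × 13 × 4 × 22) = 4.73, p = 0.030.
- Newcombe 95% interval: the difference is 0.308, with Wilson limits 0.127 to 0.576 (test) and 0 to 0.228 (control). Lower limit = 0.308 − √[(0.308 − 0.127)² + 0.228²] = 0.017. Upper limit = 0.308 + (0.576 − 0.308) = 0.576.

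The verdict on these data depends on a test that the protocol does not name.

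**5. The best possible result.** With no failures in either arm, the Wilson upper limit for each arm is z²/(n + z²), and this is also the Newcombe upper limit for the difference.
- n = 13: 3.84/(13 + 3.84) = 22.8 points.
- n = 17: 3.84/(17 + 3.84) = 18.4 points.

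**6. Would adding a margin rescue the pass rule?** Take one-sided 2.5%, 80% power and equal true rates: n per arm = (1.96 + 0.84)² × 2p(1 − p)/margin². With an assumed 95% union in both arms, margins of 10, 15 and 20 points need 75, 34 and 19 per arm. At 90% union they need 142, 63 and 36. At 98% the formula gives 31, 14 and 8, but this normal approximation is optimistic with so few failures: step 5 shows that even zero failures leaves 18 to 23 points.

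**The case against.** The strongest reply is that the protocol never equates non-significance with comparability. That is correct: a reader might infer such a rule, but the term is simply left undefined for union. The percentages in step 3 describe what follows if that reading is adopted.

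Several stronger readings are also tempting and are not supported:

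- *That the trial plans only difference tests.* Section 10.2 has a non-inferiority hypothesis with a confidence-limit rule for the primary variable, and section 10.3 provides for 95% intervals. The gap concerns secondary outcomes.
- *That the synopsis claims equality for the radiographic outcomes.* The sentence "Clinical outcome of the fracture treatment is equal between patients treated by the new bioabsorbable medical device and by standard of care" states the primary objective.
- *That section 8.1 makes significance the criterion for union.* The instruction that "statistical significance of each finding are to be reported" closes the primary objectives and follows the clinical measurements.
- *That alignment also lacks any yardstick.* It has the 10-degree threshold, although this is not tied to a confidence limit.
- *That the trial would nearly always pass the device whatever the truth.* At 40% against 5%, Fisher detects the difference in about 42% of trials at 13 per arm (100 − 57.6) and 61% at 17 (100 − 39.3). The 4-against-0 case is significant by chi-square, and its Newcombe interval excludes zero.

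It is also fair to say that union failures are monitored as adverse events and reported by group (Safety Variables; section 11), so an imbalance would be visible. A statistical analysis plan, not shown, may name the tests. Neither point removes the defect: the success rule itself is fixed in the protocol, and displaying an imbalance does not stop the objective from being declared met.

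**Conclusion.** The point holds for the union outcomes. Section 8.2 fixes a pass rule that has no margin and no confidence-limit criterion, in a trial too small to support any useful one. The firmest figure needs no assumed failure rate: with no failures in either arm, an excess of about 23 points (13 per arm) or 18 points (17 per arm) is not excluded, by the Newcombe method. The non-significance rates of 80% and 65% (Fisher), or 64% and 50% (Newcombe), rest on assumed true rates of 30% against 5% and on reading non-significance as comparability. This is a secondary objective, and the protocol ties no stopping decision to it. The change is still worth making, because it alters what the trial may conclude and is cheap.

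**What to change.** In section 8.2, replace the pass rule for the union outcomes with text such as: *Differences between groups in the proportions with delayed union, non-union and malunion will be reported with 95% confidence intervals. No claim of comparability will be based on a non-significant test. With 13 to 17 children per group, an excess of about 18 to 23 percentage points in union failure cannot be excluded even if no failure occurs.* Align the synopsis wording of the secondary objective.

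For angulation, judge the 95% confidence interval for the group difference against the protocol's own 10-degree threshold, and say so in section 8.2. That threshold is worded for deformity in a bone, so its use for a difference between groups should be stated as a choice.

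As a separate, minor matter, the synopsis primary objective should say non-inferior instead of equal, to match the alternative hypothesis in section 10.2.

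The cost is wording only: no added children, visits or measurements. The sponsor gives up a pass/fail claim on union.
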